 10.3.7.2. Subgroup Analyses53

 10.3.8. Interim Analyses53

11. References54

12. Appendices56

List of Tables

| Table | | Page |
|---------------|-------------------------------|-------------|
| Table RHCV.1. | Schedule of Activities | 12 |
| Table RHCV.2. | Objectives and Endpoints..... | 18 |
| Table RHCV.3. | Treatment Periods..... | 30 |

List of Figures

Figure

Page

Figure RHCV.1. Illustration of study design for Clinical Protocol I1F-JE-RHCV.....21

List of Appendices

| Appendix | | Page |
|-----------------|--|-------------|
| Appendix 1. | Abbreviations and Definitions..... | 57 |
| Appendix 2. | Clinical Laboratory Tests..... | 62 |
| Appendix 3. | Study Governance Considerations..... | 64 |
| Appendix 4. | Hepatic Monitoring Tests for Treatment-Emergent Abnormality..... | 69 |
| Appendix 5. | Tests for Allergic Reactions and Hypersensitivity Events..... | 70 |
| Appendix 6. | List of Excluded Medications and Procedures..... | 71 |

1. Synopsis

Title of Study:

A Multicenter, Open-Label, Post Marketing Clinical Trial to Evaluate the Efficacy And Safety Of Ixekizumab in Patients With Generalized Pustular Psoriasis (GPP) and Erythrodermic Psoriasis (EP).

Rationale:

This study is being conducted to fulfil a regulatory commitment to the Pharmaceuticals and Medical Devices Agency (PMDA) to evaluate the efficacy and safety of ixekizumab when dosed every 2 weeks (Q2W) beyond Week 12 in patients with GPP and EP.

Objective(s)/Endpoints:

| Objectives | Endpoints |
|--|---|
| 
Primary
 
 To assess the efficacy of ixekizumab Q2W beyond Week 12 in patients with generalized pustular psoriasis (GPP) and erythrodermic psoriasis (EP) | 
 Number of patients who improve their Global Improvement Score (GIS) at least 1 point from Week 12 through Week 20 and with ≤ 2 of GIS |
| 
Secondary
 
 To assess the efficacy of ixekizumab Q2W beyond Week 12 in patients with GPP and EP To assess the health outcomes of ixekizumab Q2W beyond Week 12 in patients with GPP and EP To evaluate the potential development of anti-ixekizumab antibodies of ixekizumab Q2W beyond Week 12 in patients with GPP and EP | 
The following endpoints will be assessed at each scheduled visit after Week 12:
 
 Number of patients with each GIS grade (1: Resolved, 2: Improved, 3: Unchanged, 4: Worsened) Number of patients who achieve sPGA (0, 1) and sPGA (0) Number of patients who achieve PASI 75, PASI 90, and PASI 100 from baseline Change from baseline, and percent improvement from baseline in PASI Change from baseline in PSSI in patients with scalp involvement at baseline, and percent of BSA involvement of Psoriasis Change from baseline in DLQI total score and domains, and Itch NRS score Number of patients who achieve DLQI (0, 1) and DLQI (0) Number of patients who achieve Itch NRS ≥ 4 point reduction from baseline for patients who had baseline Itch NRS ≥ 4 Number of patients who develop treatment-emergent anti-ixekizumab antibody (TE-ADA) and neutralizing anti-ixekizumab antibody (NAb) 
GPP ONLY
 
 Change from baseline on assessment of Generalized Pustular Psoriasis Severity Index at Week 12 and Week 20/ETV. |

Note: Global improvement scores will be assessed in the four grades by comparing the psoriatic findings:

(1) resolved, (2) improved, (3) unchanged, and (4) worsened. The global improvement score is assessed based on the comparison of the psoriatic findings, sPGA, PASI score, and other evaluations with those at the baseline.

Abbreviations: BSA = body surface area; DLQI = Dermatology Life Quality Index; EP = erythrodermic psoriasis; GIS = Global Improvement Score; GPP = generalized pustular psoriasis; NAb = neutralizing anti-ixekizumab antibody; NRS = Numeric Rating Scale; PASI = Psoriasis Area and Severity Index; PASI 75 = at least a 75% improvement from baseline in PASI score; PASI 90 = at least a 90% improvement from baseline in PASI score; PASI 100 = a 100% improvement from baseline in PASI score; PSSI = Psoriasis Scalp Severity Index; Q2W = every 2 weeks; sPGA = static Physician Global Assessment; TE-ADA = treatment-emergent anti-drug antibody.

Summary of Study Design:

Study I1F-JE-RHCV is a multicenter, open-label, post marketing clinical trial to evaluate the efficacy and safety of ixekizumab Q2W beyond Week 12 until Week 20 in patients with GPP and EP.

Treatment Arms and Duration:

Study I1F-JE-RHCV consists of 3 periods: a screening period of up to 30 days, a 12-week Induction Dosing Period, and an 8-week Maintenance Dosing period. All eligible patients will be administered 160 mg ixekizumab as 2 SC injections at Week 0 (baseline; Visit 2) followed by 80 mg as 1 injection at Week 2, 4, 6, 8 and 10. Patients who are inadequate responders (Global Improvement Score [GIS] ≥ 2 at Week 12 and based on the investigators' discretion) will be administered 80 mg as 1 injection at Week 12, 14, 16, and 18 or until they achieve a GIS score of 1.

Number of Patients:

A total of 12 patients will be enrolled so that at least 5 patients with EP and 5 patients with GPP who are inadequate responders (GIS ≥ 2 at Week 12 and based on the investigators' discretion) will continue to use ixekizumab beyond Week 12. Additional enrollment may occur and sample size may be increased, if no GPP or EP patients enter into Period 3 (Maintenance Dosing Period) of the study.

Statistical Analysis:

Primary analysis of efficacy, health outcome and safety measures will be conducted based on patients who continued ixekizumab 80 mg Q2W beyond Week 12 by disease type (ie, GPP and EP separately).

Baseline is defined as the last available value before the first dose in Period 2; in most cases, it will be the value recorded at Week 0 (Visit 2).

As this is a single arm study with very small sample size, no statistical inference will be performed.

Continuous data will be summarized in terms of the mean, standard deviation, minimum, maximum, median, and number of observations. Categorical data will be summarized as frequency counts.

2. Schedule of Activities

Table RHCV.1. Schedule of Activities

| Procedure | Screening Period (Period 1) | Treatment Period - Induction (Period 2) | | | | | Treatment Period - Maintenance (Period 3) | | | | ETV |
|---|-----------------------------|---|---------|---------|---------|---------|---|----------|----------|----------------|----------------|
| | V1 | V2 | V3 | V4 | V5 | V6 | V7 | V8 | V9 | V10 | |
| Study Week | - | 0 | 2 | 4 | 8 | 12 | 14 | 16 | 18 | 20 | |
| Visit Intervals | -30d to -7d | 0 | 14 ± 2d | 28 ± 4d | 56 ± 4d | 84 ± 2d | 98 ± 2d | 112 ± 2d | 126 ± 2d | 140 ± 2d | NA |
| Informed consent | X | | | | | | | | | | |
| Complete medical history | X | | | | | | | | | | |
| Demography ^a | X | | | | | | | | | | |
| Full physical examination ^b | X | | | | | | | | | | |
| Height | | X | | | | | | | | | |
| Weight | | X | | | | X | | | | X | X |
| Habits ^c | | X | | | | | | | | X | X |
| Chest X-ray ^d | X ^d | | | | | | | | | X ^e | X ^e |
| Body temperature | X | X | | | | X | | | | X | X |
| Inclusion and exclusion criteria ^f | X | X | | | | | | | | | |
| Concomitant medications | X | X | X | X | X | X | X | X | X | X | X |
| Vital sign (BP and pulse) | X | X ^g | X | X | X | X | X | X | X | X | X |
| Genetic information (Mutation of IL-36 RN) | X | | | | | | | | | | |
| Adverse event (AE/SAE/AESI) review | X | X | X | X | X | X | X | X | X | X | X |
| Administer IP | | X ^{gh} | X | X | X | X | X | X | X | | |
| Dispense IP | | X | X | X | X | X | X | X | X | | |
| IP compliance | | X | X | X | X | X | X | X | X | X | X |
| Dispense Study Drug Administration Log ⁱ | | X | X | X | X | X | X | X | X | | |

| Procedure | Screening Period (Period 1) | Treatment Period - Induction (Period 2) | | | | | Treatment Period - Maintenance (Period 3) | | | | ETV |
|---|-----------------------------|---|---------|---------|---------|---------|---|----------|----------|----------|-----|
| | | V1 | V2 | V3 | V4 | V5 | V6 | V7 | V8 | V9 | |
| Visit Number | V1 | V2 | V3 | V4 | V5 | V6 | V7 | V8 | V9 | V10 | ETV |
| Study Week | - | 0 | 2 | 4 | 8 | 12 | 14 | 16 | 18 | 20 | |
| Visit Intervals | -30d to -7d | 0 | 14 ± 2d | 28 ± 4d | 56 ± 4d | 84 ± 2d | 98 ± 2d | 112 ± 2d | 126 ± 2d | 140 ± 2d | NA |
| Collect, review, & enter data from Study Drug Administration Log | | X | X | X | X | X | X | X | X | X | X |
| Global Improvement Scores | | | X | X | X | X | X | X | X | X | X |
| PASI | X | X | X | X | X | X | X | X | X | X | X |
| sPGA | X | X | X | X | X | X | X | X | X | X | X |
| BSA | X | X | X | X | X | X | X | X | X | X | X |
| PSSi | | X | X | X | X | X | X | X | X | X | X |
| Itch NRS | | X | X | X | X | X | X | X | X | X | X |
| DLQI | | X | X | X | | X | X | | X | X | X |
| C-SSRS Baseline | X | | | | | | | | | | |
| C-SSRS Since Last Visit | | X | X | X | X | X | X | X | X | X | X |
| Self-Harm Supplement Form and Self-Harm Follow-Up Form ^k | X | X | X | X | X | X | X | X | X | X | X |
| GPP Severity Index ^l | X | X | | | | X | | | | X | X |
| Administer PPD/QuantiFERON Gold/T-SPOT ^m | X | | | | | | | | | | |
| 12-lead ECG ⁿ | X | | | | | | | | | | |
| FSH ^o | X | | | | | | | | | | |
| HIV/HBV/HCV ^p | X | | | | | | | | | | |
| HBV DNA ^q | X | | | X | X | X | | X | | X | X |
| Serum pregnancy test (Women of childbearing potential [WCBP] only) ^r | X | | | | | | | | | | |

| Procedure | Screening Period (Period 1) | Treatment Period - Induction (Period 2) | | | | | Treatment Period - Maintenance (Period 3) | | | | ETV |
|---|-----------------------------|---|---------|---------|---------|---------|---|----------|----------|----------|-----|
| | | V1 | V2 | V3 | V4 | V5 | V6 | V7 | V8 | V9 | |
| Visit Number | V1 | V2 | V3 | V4 | V5 | V6 | V7 | V8 | V9 | V10 | ETV |
| Study Week | - | 0 | 2 | 4 | 8 | 12 | 14 | 16 | 18 | 20 | |
| Visit Intervals | -30d to -7d | 0 | 14 ± 2d | 28 ± 4d | 56 ± 4d | 84 ± 2d | 98 ± 2d | 112 ± 2d | 126 ± 2d | 140 ± 2d | NA |
| Urine pregnancy test (WCBP only) ^r | | | | | | X | | | | X | X |
| Clinical chemistry | X | X | | | | X | | | | X | X |
| Hematology | X | X | | | | X | | | | X | X |
| Urinalysis | X | | | | | X | | | | X | X |
| hsCRP | | X | | | | X | | | | X | X |
| Beta-D-glucan ^s | X | | | | | | | | | | |
| KL-6 ^t | X | | | | | | | | | | |
| Immunogenicity testing ^u | | X | | | | X | | | | X | X |
| LY2439821 serum concentration ^{uv} | | | | | | X | | | | X | X |
| Pharmacogenetic sample (genetic sample/DNA) | X | | | | | | | | | | |

Abbreviations: AE = adverse event; AESI = adverse event of special interest; BP = blood pressure; BSA = body surface area; C-SSRS = Columbia- Suicide Severity Rating Scale; d = days; DLQI = Dermatology Life Quality Index; DNA = deoxyribonucleic acid; ECG = electrocardiogram; ETV = early termination visit; FSH = follicular stimulating hormone; GPP = generalized pustular psoriasis; HBcAb = hepatitis B core antibody; HBsAb = hepatitis B surface antibody; HBV = hepatitis B virus; HCV = hepatitis C virus; HIV = human immunodeficiency virus; hsCRP = high sensitivity C-reactive protein; IL-36 RN = interleukin 36 receptor antagonist; IP = investigational product; KL-6 = Kerbs von Lungren 6 antigen; NA = not applicable; NRS = numeric rating scale; PASI = Psoriasis Area and Severity Index; PCP = pneumocystis pneumonia; PPD = purified protein derivative; Ps = psoriasis; PSSI = Psoriasis Scalp Severity Index; SAE = serious adverse event; SC = subcutaneous; sPGA = static Physician's Global Assessment; TB = tuberculosis; V = study visit.

- a Demographics includes recording of year of birth, gender, and race.
- b One complete physical examination (excluding pelvic, rectal, and breast examinations) will be performed at screening. All physical examinations throughout the study should include a symptom-directed physical, as well as examination of heart, lungs, abdomen, and visual examination of the skin.
- c Habits include recording of caffeine, alcohol, and tobacco consumption.
- d A chest X-ray will be taken at screening unless one has been obtained within the past 6 months (provided the X-ray and/or report are available for review).

- e To be performed if more than 12 weeks have elapsed since the previous study X-ray was obtained. This X-ray may be performed within 12 weeks if medically indicated.
- f Patients who test positive for latent TB at screening may be rescreened following appropriate treatment as described in Section 9.4.5.2. Additionally, patients who do not qualify at screening under Exclusion Criteria [10] (active or recent infection) may be rescreened as described in Section 6.2.
- g At baseline (Week 0), BP and pulse should be measured prior to administration of the investigational product and again approximately 1 hour postadministration.
- h All patients will receive 2 SC doses of investigational product at Week 0.
- i Patients will record information in the Study Drug Administration Log, including the date, time, and location of administration of investigational product (for treatment compliance), and who administered.
- j To be collected for the patient with scalp Ps at baseline.
- k A Self-Harm Follow-Up Form is to be completed only during visits for which there is at least 1 discrete self-harm event identified on the Self-Harm Supplement Form.
- l To be collected for patients who have confirmed pustular Ps at Screening (Visit 1) and Baseline (Visit 2).
- m See Section 9.4.5.2 for detailed description of QuantiFERON Gold TB, T-SPOT.TB, and PPD testing. PPD test is performed at Visit 1, and patients will return approximately 48 and 72 hours after Visit 1 to have their PPD test read.
- n ECGs should be performed prior to injection of investigational product and collection of blood sample, as applicable. ECGs are locally performed.
- o FSH test performed for women ≥ 40 and < 60 years of age who have had a cessation of menses for at least 12 months to confirm non-childbearing potential (≥ 40 mIU/mL).
- p All patients will be tested for HBV at screening. Patients who are HBcAb+ and/or HBsAb+ at screening will have serum HBV DNA obtained by the central lab. Patients that are found to be HBV DNA positive (detectable) and/or HBsAg+ positive at screening will be excluded from the trial.
- q If patient is HBcAb+ and/or HBsAb+, HBV DNA needs to be confirmed negative at screening and at least once every month in Periods 2 and 3. (See Section 9.4.5.4).
- r To be performed for females of childbearing potential only. Urine pregnancy tests are locally performed.
- s Beta-D-glucan is required at screening and if an investigator believes it is warranted at subsequent visits, a beta-D-glucan test may be included in the work-up panel at any time during the study and may be done locally. If the beta-D-glucan test is positive, PCP needs to be ruled out. If PCP is ruled out and the investigator deems the patient fit to continue, the patient may continue in the study. If a patient has a confirmed diagnosis of PCP during the study, the patient must discontinue the study.
- t KL-6 is required at screening, and if an investigator believes it is warranted at subsequent visits, a KL-6 test may be included in the work-up panel at any time during the study and may be done locally.
- u Additional blood samples will be collected (as specified in Appendix 5) when possible for any patients who experience a potential serious allergic/hypersensitivity reaction during the study as judged by the investigator.
- v LY2439821 serum concentration will be analyzed to help facilitate the interpretation of immunogenicity data.

3. Introduction

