5.1. Overall Design

Study I1F-JE-RHCV is a multicenter, open-label, post marketing clinical trial to evaluate the efficacy and safety of ixekizumab Q2W beyond Week 12 until Week 20 in patients with GPP and EP.

The study consists of 3 periods:

- **Period 1:** Screening Period (Visit 1) lasting from 7 to 30 days prior to Period 2 (baseline; Week 0; Visit 2)

Study investigator(s) will review patient history and screening test results to determine if the patient meets all inclusion and none of the exclusion criteria to qualify for participation in the study.

- **Period 2:** Induction Dosing Period from Week 0 (Visit 2) to Week 12 (Visit 6)

All eligible patients will be administered 160 mg ixekizumab as 2 SC injections at Week 0 (baseline; Visit 2) followed by 80 mg as 1 injection at Week 2, 4, 6, 8 and 10.

- **Period 3:** Maintenance Dosing Period from Week 12 to Week 20

Responders (GIS = 1 at Week 12) will complete the study.

Inadequate responders (GIS ≥ 2 at Week 12 and based on investigators' discretion) will continue to use ixekizumab 80 mg Q2W during Period 3. If patients show a therapeutic response (GIS = 1) with 80 mg Q2W after Week 12, the patient will complete the study. Patients who complete the study before Week 20 will have an early termination visit (ETV) instead of the original scheduled visit.

Patients discontinuing from the study treatment who have received at least 1 dose of investigational product will continue to the ETV.

Ixekizumab will not be made available after conclusion of the study to patients.

Study governance considerations are described in detail in [Appendix 3](#).

[Figure RHC.V.1](#) illustrates the study design.

[figure not shown]

Figure RHCV.1. Illustration of study design for Clinical Protocol I1F-JE-RHCV.

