6.1. Inclusion Criteria

Patients are eligible to be included in the study only if they meet all of the following criteria at screening:

Type of Patient and Disease Characteristics

- [1] Present with GPP or EP based on an investigator-confirmed diagnosis and meet the associated criteria
 - [1a] GPP:
 - Meet the criteria for GPP set by Ministry of Health, Labour and Welfare (MHLW) at screening (Visit 1) and baseline (Week 0; Visit 2) regardless of IL-36 mutation status.
 - [1b] EP:
 - Diagnosed to have BSA $\geq 80\%$ involvement (with inflammatory erythema) at screening (Visit 1) and baseline (Week 0; Visit 2).
- [2] Candidates for phototherapy and/or systemic therapy

Patient Characteristics

- [3] Are at least 20 years of age at the time of screening
 - [3a] male patients:
 - agree to use a reliable method of birth control* during the study
 - [3b] female patients:
 - Are women of childbearing potential who test negative for pregnancy and agree to use a reliable method of birth control* or remain abstinent during the study and for at least 12 weeks following the last dose of investigational product, whichever is longer.
 - or-
 - Are women of non-childbearing potential, defined as:
 - Women who have had surgical sterilization (hysterectomy, bilateral oophorectomy, or tubal ligation);
 - or-
 - Women who are ≥ 60 years of age;
 - or-

Women ≥ 40 and < 60 years of age who have had a cessation of menses for ≥ 12 months and a follicle-stimulating hormone test confirming nonchildbearing potential (≥ 40 mIU/mL).

* Each of the following is considered as highly effective method of birth control:

- oral contraceptives
- condom with spermicide
- intrauterine device
- vasectomized male (with the appropriate post-vasectomy documentation of the absence of sperm in the ejaculate). For female patients in the study, the vasectomized male partner should be the sole partner for that patient.

Informed Consent

- [4] Have given written informed consent approved by Eli Lilly Japan or its designee and the Investigational Review Board/Ethical Review Board (IRB/ERB) governing the site.

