- f To be performed for females of childbearing potential only. Urine pregnancy tests are locally performed as scheduled in the SOA (Section 2). Necessary equipment may be provided centrally if needed.
- g FSH test performed for women ≥ 40 and < 60 years of age who have had a cessation of menses for at least 12 months to confirm non-childbearing potential (≥ 40 mIU/mL)
- h Immunogenicity samples will also be analyzed for ixekizumab serum concentration to facilitate in the interpretation of the immunogenicity data at Week 12 (visit 6), Week 20 (Visit 10) and ETV. In addition, a blood sample will be collected, when possible for any patient who experiences a potential systemic allergic/hypersensitivity reaction during the study as judged by the investigator.
- i Beta-D-glucan is required at a screening and if an investigator believes it is warranted at subsequent visits, a beta-D-glucan test may be included in the work-up panel at any time during the study and may be done locally. If the beta-D-glucan test is positive, PCP needs to be ruled out. If PCP is ruled out and the investigator deems the patient fit to continue, the patient may continue in the study. If a patient has a confirmed diagnosis PCP during the study, the patient must discontinue the study.
- j KL-6 is required at screening, and if an investigator believes it is warranted at subsequent visits, a KL-6 test may be included in the work-up panel at any time during the study and may be done locally.

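### No pregnancy test is scheduled at Visit 2, so the first 160 mg dose can rest on a screening test that is 7 to 30 days old

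*Protocol*

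**What the plan says.** The Schedule of Activities (protocol Section 2) has two pregnancy rows. The first, "Serum pregnancy test (Women of childbearing potential [WCBP] only", has a single mark, at Visit 1. The second, "Urine pregnancy test (WCBP only", has marks at Visit 6, Visit 10 and the early termination visit (ETV). Both rows are blank at Visits 2 to 5.

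The notes add no time point. Footnote r to the Schedule reads "To be performed for females of childbearing potential only. Urine pregnancy tests are locally performed". The matching footnote f in Appendix 2 points back to the Schedule: "Urine pregnancy tests are locally performed as scheduled in the SOA (Section 2). Necessary equipment may be provided centrally if needed".

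Section 5.1 gives the distance from screening to first dose: "Screening Period (Visit 1) lasting from 7 to 30 days prior to Period 2". The starting dose of 160 mg is given at Visit 2. The same section covers women who stop early: "Patients discontinuing from the study treatment who have received at least 1 dose of investigational product will continue to the ETV".

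On eligibility, Section 6.1 opens with "Patients are eligible to be included in the study only if they meet all of the following criteria at screening", and criterion [3b] covers women who "Are women of childbearing potential who test negative for pregnancy and agree to use a reliable method of birth control" or remain abstinent. Under Section 8.1.1 pregnancy ends treatment, and under Section 9.2.1 any pregnancy is reported through the SAE process.

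**The concern.** The protocol treats pregnancy as a bar to entry and a reason to stop treatment, yet it schedules no check on the day exposure begins. Because the inclusion criteria are tied to screening, the Visit 1 result alone satisfies [3b]. A woman who conceived after Visit 1, or shortly enough before it that the serum test was still negative, can be dosed with every scheduled procedure followed. Her pregnancy would then come to light before Week 12 only if she or the investigator noticed it, if someone ordered an unscheduled test, or if she stopped early and reached the ETV.

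The protocol re-checks other facts that can change between the two visits. Criteria [1a] and [1b] must be met at both screening and baseline, [17] looks for a suicide attempt between Visits 1 and 2, and chemistry and hematology are repeated at Visit 2. Pregnancy can change over the same interval and is not re-checked. What is at stake is fetal exposure in the individual patient; no estimate, endpoint or analysis set is touched.

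**Working it through.** The plan states no figure of its own on this point, so the check is a reading of the table followed by interval arithmetic.

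**1. Is the blank at Visit 2 real?** The Schedule has 11 visit columns (V1 to V10 and ETV). Both pregnancy rows have all 11 cells. Other rows in the same layout are marked at V2:

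| Row | Marked at |
|---|---|
| Serum pregnancy test | V1 |
| Urine pregnancy test | V6, V10, ETV |
| Clinical chemistry | V1, V2, V6, V10, ETV |
| hsCRP | V2, V6, V10, ETV |
| Inclusion and exclusion criteria | V1, V2 |
| Administer IP | V2 to V9 |

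The blank is therefore not an artefact of text extraction.

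**2. Inputs**
- V1: day -30 to day -7 (Schedule; Section 5.1)
- V2: day 0, first dose
- V6: day 84 ± 2, that is day 82 to day 86 (Schedule)
- Doses before V6: two 80 mg injections at Week 0, then one at each of Weeks 2, 4, 6, 8 and 10 (Section 5.1)

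**3. As planned**
- Age of the latest scheduled test at first dose = V2 - V1 = 7 to 30 days.
- V1 to the next scheduled test, for a patient who stays on treatment: shortest 7 + 82 = 89 days; longest 30 + 86 = 116 days.
- Dosing between those two tests: 6 occasions, 2 + 5 = 7 injections, 7 × 80 = 560 mg. Weeks 6 and 10 have a dose but no scheduled visit.

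**4. With a urine test at V2, before dosing**
- Age of the latest test at first dose = 0 days.
- V1 to V2 = 7 to 30 days; V2 to V6 = 82 to 86 days.
- Longest scheduled gap falls from 116 to 86 days (116 - 30 = 86).
- The 6 occasions and 560 mg still lie between V2 and V6. The added test does not shorten that stretch; it establishes the patient's status at its start.

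**5. How many cases might be involved?** The documents give no count of women of childbearing potential; the bounds are 0 to 12 of the 12 planned patients. As an illustration only, assume an annual pregnancy rate under contraception of 1% to 10% (not from the documents), and take the extreme of 12 such women, each with a 30-day gap:

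expected conceptions between V1 and V2 = 12 × (30/365) × 0.01 to 12 × (30/365) × 0.10 ≈ 0.01 to 0.10 in the whole trial.

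Fewer such women or shorter gaps lower this. Pregnancies already present but missed at V1 come on top and cannot be quantified from the documents.

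**The case against.** The strongest reply accepts the table reading and disputes its weight.

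- **No rule is broken.** A Visit 1 test meets [3b] as written, and neither document sets a standard requiring a repeat before dosing. This stands: it is a design choice that could be better, not a contradiction.
- **Fetal risk is not documented here.** Neither document describes reproductive risk for ixekizumab. That information would sit in the Investigator's Brochure and the package insert, which were not available, and the product is already approved in Japan for both diseases. This also stands as a limit on how strongly harm can be argued. Even so, the protocol itself requires a negative test for entry and ends treatment for pregnancy.
- **Other controls exist.** Eligibility is reviewed again at Visit 2, [3b] requires contraception or abstinence during the study and for at least 12 weeks after the last dose, [30] directs investigators to the package insert, adverse events are reviewed at every visit, and pregnancy stops treatment. These reduce the risk, but none requires a test before the first injection. The contraception clause does not reach back before study entry, so it leaves open a conception just before Visit 1. No exclusion criterion names pregnancy ([32] covers lactation), so the [3b] test is the only explicit entry check.
- **The long interval is mostly untouched by the fix.** This is correct. The 82 to 86 days and 560 mg after Visit 2 remain. The figure that bears on the proposal is the 7 to 30 day test age at first dose, and the gain is small when Visit 1 is only 7 days earlier.
- **Expected numbers are very small.** This too is correct, on the illustrative rates above.

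**Conclusion.** The concern holds. As scheduled, a woman of childbearing potential can receive her first 160 mg on a pregnancy result 7 to 30 days old. If she stays on treatment, no further test is due until 89 to 116 days after screening. These intervals follow from the Schedule's visit windows alone and need no outside assumption. What cannot be settled from the documents is how many women are affected (0 to 12) and how harmful early exposure would be; on the illustrative rates, fewer than one conception between the two visits would be expected in the whole trial. This is a recommended safety improvement, not a flaw that threatens the study. It has no bearing on the GIS endpoint, the secondary endpoints or any analysis in the SAP.

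**What to change.** In the Schedule of Activities, mark the local urine pregnancy test at Visit 2 for women of childbearing potential, and state that it is read before the first injection. In Section 6.1, have [3b] require a negative pregnancy test at screening and at baseline (Week 0; Visit 2), the form that [1a] and [1b] already use. The eligibility review already scheduled at Visit 2 is the natural place to act on the result.

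The cost is one mark in the Schedule, a few words in [3b], and one dipstick per woman concerned at an existing visit. Urinalysis is not scheduled at Visit 2, so the urine sample is an extra one, with a small kit cost and a few minutes' wait before dosing. No new visit, staff or invasive procedure is needed.

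The change has limits. A urine test can miss a very recent conception, and a Visit 2 test does nothing about conceptions after Visit 2.
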